Delay discounting task	X	X	X	X	X	X			
N back test	X	X	X	X	X	X			
Stroop Test	X	X	X	X	X	X			
Young Mania Rating Scale	X	X	X	X	X	X			
DKEFS Verbal Fluency Test	X	X	X	X	X	X			
Pressure pain threshold	X	X	X	X	X	X			
Sham validating measure				X					
Trail making A and B	X	X	X	X	X	X			
Visual Analog Scales**	X	X	X	X	X	X			
MINI International	X								
Neuropsychiatric Interview (MINI)									
Randomization	X								

^{**} This assessment will be collected 3 times per day pre and post rTMS.

Safety Assessments

Research staff will use the MedDRA System Organ Class (SOC) and preferred term (PT) to document adverse events, which will be assessed at each treatment, and at follow-up visits.

This protocol will not modify patient care and our visits will not interfere with regular clinical care, except in the case of imminent danger to the patient or others in which appropriate measures will be taken, like contacting the primary treatment team and placing the patient on 1:1 observation until evaluation by the primary team.

STUDY POPULATION

Participant recruitment will occur at the inpatient units at the Psychiatric Research Institute (PRI). Target sample size is 20, which will be randomized into active or sham groups (1:1). Considering 40% attrition rate we plan to recruit 28 participants.

Recruitment: Recruitment will be facilitated by the PI's role of PRI inpatient attending physician. The success of this proposal depends heavily on the ability to recruit patients very soon after hospitalization for

PI: [name]

suicide ideation or behavior.

All participants will be compensated \$40 for their participation in each of the 3 rTMS sessions of the active phase of the study and the 2 follow-up sessions. Participants can earn a total of \$200 for completing the entire study, including both follow up visits.

Inclusion Criteria

- a) Age 18-60 years, of all races and ethnicities;
- b) Admitted voluntarily to the adult psychiatric inpatient at PRI;
- c) Suffering from a current depressive episode as defined by the DSM-V
- d) Currently have diagnoses of major depressive disorder
- e) Reason for hospitalization should be a recent suicide attempt or suicidal ideation
- f) Current severe suicidal ideation defined by a score >7 in the Beck Scale for Suicidal Ideation
- g) Must pass the TMS safety checklist (TASS)
- h) Women of childbearing age must have a negative result on a pregnancy test
- i) Ability to read, write and speak English.

Exclusion Criteria

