- a) History of dementia, neurovascular or neurodegenerative conditions
- b) Physical disabilities that prohibit task performance (such as blindness or deafness)
- c) Patients must not have increased intracranial pressure, which may increase seizure susceptibility.
- d) Implanted medication pumps of any type
- e) Intracardiac lines
- f) Significant heart disease, defined as heart disease that causes moderate to severe symptoms and/or is characterized by moderate to severe pathology, including a recent history of myocardial infarction and heart failure with an ejection fraction of less than 30% or with a New York Heart Association Functional Classification of Class III or IV.
- g) Choosing to opt out of the research study.
- h) Additional exclusion criteria for rTMS include the following:
 - i. a personal history or 1st degree relative with history of epilepsy;
 - ii. a personal history of head injury, aneurysm, stroke, previous cranial neurosurgery, neurological, or migraines;
 - iii. recent use of cocaine or alcohol;
 - iv. ferromagnetic metal implants in the head or neck, active or inactive implants(including device leads), deep brain stimulators, cochlear implants or vagus nerve stimulators;
 - v. a pacemaker;
 - vi. pregnancy (or the possibility of pregnancy);
 - vii. Medications that lower seizure threshold (bupropion or tricyclic antidepressants, such as thorazine, clozapine, amitriptyline, amoxapine, Norpramin, Sinequan, Tofranil, Pamelor, Vivactil, or Surmontil). Other antidepressant and antpsychotic medications have been deemed exhibit a relatively low seizurogenic potential (Pisani et al. 2002).
 - viii. Patients taking a medication for weight loss and depression called bupropion (Wellbutrin) they will be excluded because it may increase the likelihood of experiencing a seizure.

Of note, patients on a current depressive episode with a diagnosis of bipolar disorder will be eligible to participate in this study for several reasons. Many patients suffering from depression are not diagnosed with bipolar until an eventual manic episode. Bipolar disorder by itself has not been associated with higher risk for seizures. Many patients with major depression or bipolar depression receive antipsychotics not only for psychotic symptoms but also as adjuvant treatment. Lastly,

PI: [name]

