- 1. Seizures: Seizure induction represents the most serious known risk of TMS (26). Seizures have been reported more frequently in subjects with brain lesions (e.g., stroke) but have rarely been reported in subjects with no history of seizures or neurologic disease. When seizures have been reported, they were almost exclusively in association with a stimulation frequency >1 Hz. Based on an extensive review of the literature, guidelines have been developed that specify the number of stimulations that may safely be given as a function of stimulus intensity (% of Motor Evoked Potential [MEP]) and frequency of stimulation (29). Using these guidelines, there have been few published reports, to our knowledge, of seizures or evidence of after discharge or spread of excitation in normal subjects receiving repetitive TMS who did not have an identified risk factor that is exclusionary for our study (26). We propose to adhere to the published guidelines. Furthermore, as subjects with a history of seizures are more likely to experience seizures due to TMS, these subjects will be excluded.
- 2. Effects on Cognition: A number of studies have been performed to identify possible adverse neuropsychological consequences of TMS. There have been several studies in which a number of cognitive tasks were administered before and after TMS (29, 30). Few adverse effects of TMS on cognition are reported, and there is a trend for performance to be better on measures such as delayed story recall. Two studies, however, have demonstrated possible adverse effects lasting up to one hour. Greenberg et al. (cited in (29)) reported that task switching was impaired after 20-Hz stimulation of the right compared to the left dorsolateral frontal lobe. As there was no untreated condition, this effect may reflect an enhancement of function after the left prefrontal TMS rather than a decrement after right TMS (see Grafman et al. (31)). Flitman et al. (32) reported a significant decrease in logical memory one hour after testing after extensive stimulation using

PI: *[name]* parameters that exceed guidelines for inter-train interval (150 trains of rTMS at 15 Hz, 750 msec duration, and 1.2 times the MEP).

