- 7. Kindling: Kindling is a process by which repeated administration of an initially subconvulsive stimulus results in a progressive intensification of induced neuroelectrical activity resulting in a seizure. This has not been reported with TMS and appears unlikely for several reasons. Kindling is most readily obtained with high-rate repetitive stimulation (e.g., 60 Hz), requires a pulse duration of 1 msec (longer than that of TMS), and is easiest to produce in

PI: [name]

the amygdala and hippocampus. Kindling of the neocortex in animal models of epilepsy is very difficult to achieve. There is no evidence that kindling can be produced by TMS.

- 8. Exposure to Magnetic Fields: The maximal field strength generated by commercially available stimulators, such as the NeuroStar TMS Therapy System and NeuroStar XPLOR Clinical Research System machine to be used in our laboratory, is in the 2-Tesla range. We typically deliver between 50% and 70% of the maximum output in our studies. The field is induced for a brief period only, and the strength of the field falls off rapidly with distance from the coil (negligible at >2 cm). There is no evidence of adverse effects from magnetic field exposure during TMS.
- 9. A seizure caused by rTMS could place subjects at financial risk secondary to cost of medical care. Having a seizure might also influence driving privileges, employment, and the ability to obtain insurance. Subjects are informed of these risks in the consent process. The PIs would provide documentation that the seizure was triggered by rTMS, that it does not constitute epilepsy, and that seizures caused by rTMS have not resulted in future seizures. Seizures induced during electroconvulsive therapy (ECT) for depression, for example, do not cause driving privileges to be revoked in the state of Arkansas. Like ECT, a seizure occurring after rTMS would not cause driving privileges to be revoked.
- 10. There is a risk of a syncopal/convulsive syncopal event. Information regarding a history of syncope will be requested during the screening process. Subjects will be monitored for signs/symptoms during rTMS including blood pressure monitoring. Should an event occur, the treatment will be immediately stopped, subjects reclined and legs will be elevated.

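### The risk section says people with a history of seizures are excluded, but the exclusion list has no matching item: on seizure history it names only epilepsy

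*Combined protocol and SAP*

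**What the plan says.** All references are to the combined protocol and SAP.

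- **Risks Associated with TMS, item 1 (Seizures).** Seizure is presented as the gravest known hazard of the technique. The item closes by saying that "as subjects with a history of seizures are more likely to experience seizures due to TMS, these subjects will be excluded". The statement is not limited to epilepsy.
- **Exclusion Criteria, h) i.** The only listed item on seizure history is "a personal history or 1st degree relative with history of epilepsy".
- **Exclusion Criteria, h) ii.** "a personal history of head injury, aneurysm, stroke, previous cranial neurosurgery, neurological, or migraines". One entry is an adjective with no noun.
- **Inclusion Criteria, g).** "Must pass the TMS safety checklist (TASS"). The checklist's questions and its pass rule are not given.
- **Risks Associated with TMS, item 9.** If a seizure occurs, the investigators would document "that the seizure was triggered by rTMS, that it does not constitute epilepsy".
- **Protection Against Risks Associated with TMS.** The opening text relies on the exclusion criteria to remove people at greater risk.

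**The concern.** Eligibility is decided by the inclusion and exclusion lists. A sentence in a risk narrative does not exclude anyone unless a criterion carries it out. Here the narrative describes an exclusion for any seizure history, and the list does not contain it.

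The primary objective of the trial is safety, and seizure is the hazard that the protocol ranks highest. Item 12 of the same risk section adds that the listed risks are increased because the 5-second trains exceed the 4.2-second limit it attributes to the FDA. The reassurance in item 1 concerns people without a risk factor that this study excludes. If the list admits people with a past seizure, that reassurance does not describe the enrolled population. A seizure in such a person would also be hard to interpret in the safety report, because one part of the protocol says that the person should not have been enrolled.

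**Working it through.** There is no stated figure to reproduce, and no arithmetic applies. The check is to take a defined patient through the criteria.

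**Test case.** One provoked seizure some years ago, no epilepsy diagnosis, no affected first-degree relative, and no other relevant condition or current exposure.

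| Criterion | Does it exclude the test case? |
|---|---|
| Exclusion a) dementia, neurovascular or neurodegenerative disease | No |
| Exclusion c) raised intracranial pressure | No |
| Exclusion h) i, epilepsy | Not by its wording |
| Exclusion h) ii, named entries: head injury, aneurysm, stroke, cranial neurosurgery, migraine | No |
| Exclusion h) ii, the unfinished entry in "previous cranial neurosurgery, neurological, or migraines" | Cannot be determined |
| Exclusion h) iii, "recent use of cocaine or alcohol" | No, if the exposure is not recent |
| Exclusion h) vii and viii, "Medications that lower seizure threshold" and bupropion | No, if not currently taken |
| Inclusion g), TMS safety checklist | Cannot be determined |

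The remaining exclusions (physical disability, implants, lines, pacemaker, heart disease, pregnancy, opting out) do not bear on seizure history.

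**Can epilepsy in h) i be read to include any past seizure?** The protocol's own usage is against it. Item 9 says that a seizure triggered by rTMS is not epilepsy, so the authors use the two words for different things. The word in h) i therefore cannot be assumed to cover the wider group in item 1.

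**Does another screening step supply the rule?** Past medical history is collected after consent, and records may be reviewed to confirm candidates. Both steps gather information, but neither states that a past seizure is disqualifying. Item 10 of the risk section says that a history of syncope will be asked about at screening. No equivalent sentence exists for seizures.

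**Result.** No clearly worded exclusion removes the test case. Two criteria might: the unfinished entry in h) ii and the checklist in inclusion g). The documents do not allow either to be resolved.

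**The case against.** The strongest reply is that the list is much wider than epilepsy. It bars raised intracranial pressure expressly because of seizure susceptibility. It also bars head injury, stroke, cranial neurosurgery, recent cocaine or alcohol use, and drugs that lower the seizure threshold. These items would remove many people with a past provoked seizure. The checklist is itself a listed criterion and may well ask about seizures. Its absence from Tables 1 and 2 proves little, since the pregnancy test, also an eligibility requirement, is missing from both as well. The lost noun in h) ii might be a drafting slip or an effect of reading the PDF, and the completed entry might cover the case.

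All of this stands, and it limits the point. A reader might infer that a patient with a past seizure does pass the criteria and does receive active stimulation. The documents do not support that. Two criteria are unresolved, the risk section says that such patients are excluded, and allocation is 1:1 between active and sham. A reader might also want a count of affected recruits, but the documents give no rate of seizure history, and part of any such group would be removed by the other items. Nor would one seizure dominate the planned safety comparison: that is a Fisher's exact test on the number of subjects with any adverse event, to which one seizure adds at most one subject.

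None of this removes the mismatch. The risk section states an exclusion, and the exclusion list does not contain it.

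**Conclusion.** The point holds as an internal contradiction: the plan is wrong as written. The risk section excludes any history of seizures, while the operative list names only epilepsy and leaves a neighbouring entry unfinished. A past seizure without an epilepsy diagnosis may pass the exclusion list, and the patient may be randomised to active rTMS. Whether this would happen in practice depends on the checklist in inclusion g), whose content is not in the documents.

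The size cannot be put in numbers of patients. The importance rests on three statements in the protocol: safety is the primary objective, seizure is the most serious known risk, and the exclusion criteria are relied on to remove people at higher risk. The conclusion assumes that staff apply the criteria as worded and that epilepsy carries the narrower meaning that item 9 gives it.

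**What to change.** The sponsor and the investigator should reconcile three places: the inclusion criteria, the exclusion criteria and item 1 of the TMS risk section. The eligibility list and the risk section should state the same seizure-history rule. What that rule should be is for them to decide. The unfinished entry in exclusion h) ii should be completed. If the TMS safety checklist is the intended safeguard for seizure history, the criteria should say so.

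The cost is a wording amendment submitted to the IRB. A few candidates may be lost, but they are people whom the protocol already says it excludes. No change to the design, sample size or analysis is needed.

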TMS is a noninvasive method to cause depolarization or hyperpolarization in the neurons in the brain using electromagnetic induction to induce weak electric currents using a rapidly changing magnetic field. TMS is a novel intervention developed in the field of neurology that has been used in the treatment of patients suffering from migraine, stroke, Parkinson's disease, tinnitus and depression. In healthy subjects, high frequency rTMS over the left DLPFC has been shown to alter impulsive choice behavior (to decrease delay discounting) in healthy individuals and in smokers (12). On the other hand, a trial of TMS by one of the leaders in the field has shown it to be safe and well tolerated in recent suicide attempters suffering from depression with comorbid post-traumatic stress disorder and traumatic brain injury (13).

UAMS investigators have used repetitive transcranial magnetic stimulation (rTMS) to understand and treat phantom sound perception in subjects with tinnitus and to examine risky choices and impulsive behaviors using delay discounting in smokers. We propose to replicate a randomized controlled trial of rTMS over 3 days in a sample of well characterized acutely suicidal inpatients.

Our overall hypothesis is that 10 Hertz rTMS of the left dorsolateral prefrontal cortex (DLPFC) will correct impulsive choice behavior deficits found in acutely suicidal patients that in turn will translate into faster resolution of acute suicidal ideation. The current proposal will expand our understanding of the neurobiology of suicidal behavior by examining a potential neurocognitive mechanism of acute suicidality and test the value of rTMS as intervention for acute suicidal behavior. The current proposal will utilize behavioral assessments and rTMS in a randomized controlled trial in a group of adult patients hospitalized: a) following a recent suicide attempt with persistent suicidal ideation, or b) for severe suicidal ideation (n=20). To meet this goal we plan to recruit up to 28 individuals. Specifically, we propose:

The primary objective/endpoint of this study is safety. Adverse events will be collected throughout the duration of the trial. Any subject that meets the criteria for withdrawal (*Safety Assessments, page 14*) will be withdrawn from the study. The study will be stopped and all subjects withdrawn if two completed suicides by subjects receiving TMS occur during the active TMS treatment.

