3. Effects on Mood: Dysphoria with crying has been induced after left prefrontal stimulation (33). In contrast, high-frequency stimulation of the right prefrontal cortex may transiently improve mood as rapid-rate rTMS has been shown to be a safe and effective treatment in subjects with depression.

Since this study aims to assess the effect of rTMS on suicidal ideation, all subjects will be experiencing suicidality by definition. Hence, subjects will already be under ongoing intensive psychiatric inpatient care with suicide precautions. To assess worsening of suicidal ideation we will perform daily assessments and share with the treatment team in case of worsening of suicidal ideation.

There is a risk of worsening depression as a result of rTMS treatment. The subjects are inpatient and will be assessed daily by the treatment team and followed up 3 and 6 months after treatment. If worsening depression occurs during the study, the treatment will be stopped and the subject will be withdrawn from the study.

There is a risk of mania/hypomania in subjects with or without bipolar disorder. Also the use of rTMS may increase the risk of suicide or suicidal ideation. Subjects will be assessed daily for the development of mania or hypomania with the Young Mania Rating Scale. If mania/hypomania develops during the study, the subject will be withdrawn from the study and the treatment team will be informed in order to initiate adequate treatment. This would represent a relatively minor adjustment since all subjects will already be inpatient in the psychiatric ward.

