- 8. Pregnancy tests results from medical records will be obtained for women who are of childbearing age and for whom a possibility of pregnancy is indicated.

PI: [name]

Protection Against Risks Associated with Loss of Confidentiality

All data will be safe-guarded in accordance with HIPAA. The investigators use codes to keep subject information secure. Data encryption software is required at UAMS for computers with confidential information. All study staff will have current documentation of HIPAA and CITI training.

Protection Against Risks Associated with Interviews and Questionnaires

Subjects may decline to answer any questions that may make subjects uncomfortable, including questions that may be asked of subjects by the study physician. Subjects may be excluded if the information is necessary to prevent adverse events associated with study procedures.

Protection Against Risks Associated with Blood Draw

Blood draws will be performed by trained staff in an appropriate setting to minimize adverse risks.

Potential Benefits

Suicidal ideation and behavior are very distressing and we anticipate that subjects will be eager to participate in this study with the hope of reducing suicidal ideation. This study will allow us to gather important data with regard to the anticipated efficacy of rTMS for the alleviation of suicidal ideation, thus being of benefit to all subjects who suffer from suicidal ideation.

SAFETY ASSESSMENTS

Safety monitoring will include the following: 1) the PI is the designated responsible entity; 2) subjects will be videotaped during rTMS in order to have a visual record of seizure activity if it occurs (we turn on a WebCam during each rTMS session and discard data if no adverse event occurs); 3) during and immediately following stimulation, subjects will be inspected for signs of twitching and movement indicative of seizure by the study physician or nurse; 4) in the event of seizure, the plan outlined under protection against risk will be followed by study personnel; 5) the PI will report any adverse events to the IRB and funding agency Any seizure resulting from this study would immediately be published so as to add to the collective body of information on TMS. The PI will prepare regularly scheduled reports to the IRB, as required, in a timely fashion.

Subjects will be withdrawn from the study if:

- they experience a seizure or a reaction to rTMS that looks like a seizure
- experience severe pain, like dental pain

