- hearing gets worse during or after stimulation
- syncope during rTMS
- develop mania or hypomania during the TMS trial

The study will be stopped and all subjects withdrawn if two completed suicides by subjects receiving TMS occur during the active TMS treatment- as suggested by the FDA.

Adverse Events Reporting and Evaluation

All adverse events occurring during the course of the clinical study, whether device-related or otherwise, will be recorded on the Adverse Event Case Report Form. For all adverse events, the investigator will provide an assessment of the adverse event, its treatment and resolution, and its relationship to the investigational device. Special reporting procedures are required for certain adverse events.

PI: [name]

Identification of Adverse Events

An adverse event is defined as any new medical problem, or exacerbation of an existing problem, experienced by a subject while enrolled in the study, whether or not it is considered drug/device-related by the investigator.

Relationship of Adverse Events to the Investigational Device

The investigator will assess the relationship of the adverse event to the investigational device. The relationship will be assessed using the following categories:

- Definitely Related: A direct cause and effect relationship between the investigational drug or device/experimental treatment and the adverse event exists.
- Possibly Related: A direct cause and effect relationship between the investigational drug or device/experimental treatment and the adverse event has not been clearly demonstrated, but is likely or very likely.
- Unlikely Related: A direct cause and effect relationship between the investigational drug or device/experimental treatment and the adverse event is improbable, but not impossible.
- Unrelated: The adverse event is definitely not associated with the investigational drug or device/experimental treatment.

Unanticipated Adverse Device Effects

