The Principal Investigator will carefully monitor study procedures to protect the safety of research subjects, the quality of the data and the integrity of the study. To protect the identity of research volunteers, contact information will be stored in a separate file and locked cabinet, away from experimental data forms. All study subject material will be assigned a unique identifying code or number. The key to the code will be kept in a locked file in the Study Coordinator's office. Only [name] and designated research staff will have access to the code and information that identifies the subject in this study. All experimental data will be identified using a study code rather than a name, social security number, or other identifying information. All data collection forms will be kept in a locked cabinet in the Psychiatric Research Institute. Computer data records will remain on UAMS maintained password protected network drives.

DATA ANALYSIS

Cognitive tests and questionnaires

Data will be scored and analyzed/summarized according to instructions. Scores will be analyzed via t-tests, analysis of variance (ANOVA) or regression analysis.

PI: [name]

The primary outcome (impulsive choice measured by delay discounting) will be analyzed using an MMRM (mixed model repeated measures) approach based on a modified intent-to-treat (mITT) population. The mITT population will be defined as randomized subjects who started at least one treatment. Participants from the mITT population who are included in the MMRM model will also require both a baseline and at least one post- baseline SSI score. The model will include as the dependent variable change from baseline in delay discounting indifference point (K) at each post-baseline visit during the acute phase. Independent variables in the MMRM model will include treatment, visit, treatment-by-visit interaction, delay discounting at baseline, gender, age at baseline and diagnosis. Visits (Days 0, 1, 2, 3) will be treated as a categorical variable. Unstructured variance-covariance structure will be used. This same analysis will also be repeated on the completers' population, defined as subjects who completed 3 days of treatment with the scheduled maximum 6000 pulses per session.

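### Listed harms lead to withdrawal from the study, and the plan provides no later assessments, adverse event collection or 3- and 6-month visits for those subjects

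*Combined protocol and SAP*

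**What the plan says.** Background and Rationale states: "The primary objective/endpoint of this study is safety". It then points to the withdrawal criteria.

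Those criteria appear in two places:
- **Risks Associated with TMS, Effects on Mood.** On mania: "If mania/hypomania develops during the study, the subject will be withdrawn from the study". On depression: "If worsening depression occurs during the study, the treatment will be stopped and the subject will be withdrawn from the study".
- **Safety Assessments (the section after Risks and Benefits).** The list opens with "Subjects will be withdrawn from the study if" and names seizure or a seizure-like reaction, severe pain, worse hearing, syncope, and subjects who "develop mania or hypomania during the TMS trial".

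On adverse events, the Safety Assessments paragraph under Study Design and Procedures refers to events "which will be assessed at each treatment, and at follow-up visits". Identification of Adverse Events limits the definition to problems "experienced by a subject while enrolled in the study". Adverse Events Reporting and Evaluation has every event recorded, with its treatment and resolution.

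On analysis, Data Analysis says: "The mITT population will be defined as randomized subjects who started at least one treatment". To enter the MMRM for delay discounting, an mITT subject must also have an SSI score at baseline and one or more afterwards. Follow-up outcomes are analysed by MMRM on change at each follow-up visit and by repeated measures ANOVA at 3 and 6 months. Time to re-admission is compared by log-rank test, and the occurrence of any adverse event by Fisher's exact test.

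**The concern.** Stopping a treatment and ending observation are different acts, and the plan joins them for the subjects whose later course matters most to a safety objective. Effects on Hearing names a risk of permanent hearing loss, but worse hearing ends participation, so no scheduled visit would show whether it persisted. Effects on Mood says that rTMS may raise the risk of suicide or suicidal ideation, but a subject withdrawn for mania or worsening depression has no planned 3- or 6-month C-SSRS.

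The data are then absent because of how the subject fared. Follow-up results would describe those who met no withdrawal criterion, and no missing-data method or sensitivity analysis is given for the 3- and 6-month analyses.

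**Working it through.** **1. Is withdrawal from the study just another way of saying that rTMS stops?** The sentence on worsening depression names both acts, stopping treatment and withdrawing the subject. Read as written, they are separate. Also, Table 2 schedules the first HAM-D after baseline once session 3 of day 3 is over. The treatment team assesses patients daily and may see worsening sooner. But withdrawal for worsening first seen on that HAM-D stops no stimulation and only removes later data.

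**2. What is kept and what is not?**

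| Data on a subject withdrawn for a listed harm | Provided for? |
|---|---|
| The triggering event, its treatment and resolution | Yes (Adverse Events Reporting and Evaluation) |
| Serious events and deaths | Own reporting rules |
| Contribution to the Fisher test | Yes, counted as a subject with an event |
| Later, new adverse events | No: events are elicited at study visits and defined during enrolment |
| Remaining Table 2 assessments, including before discharge | No provision |
| 3- and 6-month visits | No provision; the depression paragraph in Effects on Mood mentions both follow-up and withdrawal without reconciling them |

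**3. Effect on each analysis.**
- Follow-up MMRM: the dependent variable is change at each follow-up visit. A subject with no follow-up visit contributes nothing.
- Repeated measures ANOVA: in its standard form it drops subjects with incomplete visits.
- Log-rank test for re-admission: if observation ends at withdrawal, censoring may be related to risk. The documents do not say where re-admission data come from.
- Delay-discounting MMRM: SSI is not defined. The apparent reading is the Beck Scale for Suicidal Ideation, since the source cited for that scale describes the Scale for Suicide Ideation. Table 2 gives that scale at intake, after session 3 on day 3, before discharge and at follow-up, but gives delay discounting at every time point. A subject withdrawn on day 1 or 2 can therefore have delay-discounting values after baseline but no SSI score after baseline. That subject is in the mITT set but fails the MMRM inclusion condition. The completers' analysis excludes the subject too.

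**4. Scale.** The plan's only figure on loss is its recruitment target: 20 × (1 + 0.40) = 28, which reproduces the stated 28. At 40% attrition, 28 × (1 − 0.40) = 16.8 would remain, which is below 20. In any case, an allowance for how many leave does not address who leaves.

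With 20 subjects at 1:1 there are 10 per arm, so one subject is 1/10 = 10% of an arm.

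As an illustration only, assume a later-event risk of 10% in subjects who stay and 20% to 50% in those withdrawn, with 1 to 3 of 10 withdrawn. None of these inputs is in the documents.
- Low end: true arm risk (1 × 0.20 + 9 × 0.10)/10 = 11%; share of expected later events unseen 0.20/1.10 = 18%.
- High end: (3 × 0.50 + 7 × 0.10)/10 = 22%; share unseen 1.50/2.20 = 68%.
- The risk observed in those who stay is 10% in both cases.

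**5. Do the two withdrawal passages agree?** Worsening depression is a reason under Effects on Mood but is absent from the Safety Assessments list. Mania counts at any time in the study under Effects on Mood, and during the TMS trial in the Safety Assessments list. Under Effects on Mood, mania found at month 3 would remove the month 6 visit; under the list it arguably would not.

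**The case against.** The strongest reply is that a reader might infer that the safety data of harmed subjects are lost, and the documents do not say that. The triggering event is recorded with its treatment and resolution, serious events and deaths are reported separately, and the event counts in the planned between-group safety test. This stands. What it leaves open is how resolution, or anything later, would be observed once no contact is scheduled.

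Other stronger readings also fail:
- *That every harmed subject is removed.* Only listed harms trigger withdrawal. Worsening suicidal ideation has no withdrawal rule; it is assessed daily and shared with the treatment team.
- *That data collection after withdrawal is prohibited.* The documents are silent; they do not forbid it.
- *That the result is biased in favour of rTMS.* In the Fisher test, a withdrawal for harm counts against the arm in which it occurs. Follow-up means could favour active treatment if its losses were larger and those lost did worse, but neither is known, and similar losses under sham could offset the shift.
- *That the bias can be set against the planning effect of d=0.23.* That figure is a difference in the delay-discounting rate K between two patient groups. No target effect is given for depression or ideation scores, and any assumed shift would be unsourced.
- *That the missing-at-random assumption is violated by definition.* Missingness caused by harm violates it only if it still depends on the unseen values after conditioning on the data in the model. The fair point is narrower: the harm measures are not in the delay-discounting model. Where a withdrawn subject does enter that model, the earlier visits are kept.

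**Conclusion.** The point holds as a gap in follow-up. Subjects who meet a listed criterion are withdrawn from the study, and no provision keeps their later assessments, adverse event collection or 3- and 6-month visits. In a trial with safety as its primary objective, the later data then go missing for a reason related to outcome. The follow-up MMRM and ANOVA would describe selected patients, and re-admission times may be informatively censored.

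The exclusion of subjects withdrawn on day 1 or 2 from the delay-discounting MMRM rests on reading SSI as the Beck scale and on no assessment being made after withdrawal.

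The number withdrawn and how they would have fared are unknown, so neither the size nor the direction of bias can be derived. The one firm figure is that each subject is 10% of a planned arm. The matter should be corrected, but it does not undermine the recording of the events themselves.

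**What to change.** Leave all clinical stopping rules as they are, and add the following:
1. A subject who meets a withdrawal criterion stays under observation for the assessments already scheduled, for adverse event collection and for the 3- and 6-month visits, unless consent is withdrawn. Such a subject counts as enrolled for the adverse event definition.
2. These data enter the mITT and safety analyses.
3. Inclusion in the delay-discounting MMRM depends on a delay-discounting value after baseline, not on an SSI score.
4. Effects on Mood and the Safety Assessments list are reconciled on worsening depression and on the period in which mania leads to withdrawal. Which version is right is for the investigators to decide.

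The cost is a protocol amendment with IRB approval and a few more follow-up contacts. The visits themselves are already in Table 2.
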